11.5 Analysis of ECG Parameters

The ECG parameters will be assessed as scheduled in the study protocol.

Summary statistics for mean change from baseline for corrected QT interval (QTc) using Bazett (QTcB) and Fridericia (QTcF) corrections, aggregated, will be provided by analysis visits.

- Values for both QTcF and QTcB interval measurements will be categorized into the following: ≤ 450 ms, > 450 ms, > 480 ms, > 500 ms, or missing. For the scheduled visits, as well as baseline, the number and percentage of subjects within each category will be presented. Additionally, for each category, the number and percentage of subjects with a maximum QTcF interval falling into the category will be presented; a similar summary will be presented for QTcB intervals.
- For QTcF and QTcB intervals, the changes from baseline will be categorized into the following: < 30 ms, $30 \leq - < 60$ ms, ≥ 60 ms, or missing. For the scheduled visits, the number and percentage of subjects within each category will be presented. Additionally, for each category, the number and percentage of subjects with a maximum change from baseline in the QTcF interval falling into the category will be presented; a similar summary will be presented for QTcB intervals.

Analyses will be conducted in the Safety_A1 Population, the Safety_B_R Population, and the ALL_RZB Population.

11.6 Local Tolerability

Local tolerability of the subcutaneous injection will be assessed by the investigator according to 6 items: swelling, induration, heat, redness, pain, and other findings. Proportion of subjects reporting each condition will be summarized.

Local tolerability will be summarized in the Safety_A1 Population and the Safety_B_R Population. In addition, the overall rate (with at least one occurrence) during the study will also be presented in the ALL_RZB Population.

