Complete safety tables will be provided for the Safety_A1 Population and the Safety_B_R population. Only AE overview tables will be provided for other safety populations.

The Safety Population will be analyzed based on the actual treatment received at the randomization visit (Part A) and at the re-randomization visit (Part B).

In addition, an All Risankizumab Treated Population (ALL_RZB) is defined as all subjects who receive at least one dose of risankizumab in the study. The ALL_RZB Population will be used for safety analyses. Complete safety tables will be provided in the ALL_RZB Population.

Table 1. Notations for Treatment Groups

Population	Treatment Code	Definition
ITT_A1/PP_A1/ Safety_A1	RZB	Subjects who randomized to risankizumab 150 mg.
	PBO	Subjects who randomized to placebo.
ITT_A2/Safety_A2	RZB/RZB	Subjects who randomized to risankizumab 150 mg.
ITT_ARM2/ Safety_ARM2	PBO/RZB	Subjects who randomized to placebo and received at least one dose of study drug on or after Week 16.
ITT_B_R/PP_B_R/ Safety_B_R	RZB/RZB/RZB	Subjects who re-randomized to risankizumab 150 mg at Week 28.
	RZB/RZB/PBO	Subjects who re-randomized to placebo at Week 28.
ITT_B_NR/Safety_B_NR	RZB/RZB/RZB	Subjects who randomized to risankizumab and are non-responders at Week 28.
ITT_B_PBO_RT/ Safety_B_PBO_RT	RZB/RZB/PBO/RZB	Subjects who received open-label risankizumab 150 mg as retreatment, after re-randomized to placebo in Part B.
ITT_B_RZB_RT/ Safety_B_RZB_RT	RZB/RZB/RZB/RZB	Subjects who received open-label risankizumab 150 mg as retreatment, after re-randomized to risankizumab in Part B.
ALL_RZB	RZB	Subjects who received at least one dose of risankizumab 150 mg.

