Table 12. Visit Windows for Analysis of Other Efficacy Endpoints Collected at Week 28, 52, 76, and 104 in Part A2 and B (ITT_ARM2 Population)

Window Label	Target Day	Interval
Entry of A2	1	≤ 1
Week 28	85	[2, 169]
Week 52	253	[170, 337]
Week 76	421	[338, 519]
Week 104	617	[520, 715]

Rx Day calculated relative to first dose date of risankizumab.

Table 13. Visit Windows for Analysis of PASI and sPGA During Retreatment with Risankizumab (ITT_B_PBO_RT/ITT_B_RZB_RT Populations)

Window Label	Target Day	Interval
Entry of RTS	1	≤ 1
Week 8R	57	[2, 85]
Week 16R	113	≥ 86

Rx Day calculated relative to first dose date of retreatment with risankizumab.

Table 14. Visit Windows for Analysis of Other Efficacy Variables Only Collected at EOT and EOO Visits During Retreatment with Risankizumab (ITT_B_PBO_RT/ITT_B_RZB_RT Populations)

Window Label	Target Day	Interval
Entry of RTS	1	≤ 1
Week 16R	113	≥ 2

Rx Day calculated relative to first dose date of retreatment with risankizumab.

Table 15. Visit Windows for Analysis of Vital Signs and Local Tolerability in the ALL_RZB Population

Window Label	Target Day	Interval
Baseline	1	$\leq 1^a$
Week 4	29	[2, 43]
Week 8	57	[44, 71]
Week 12	85	[72, 99]
Week 16	113	[100, 155]
Week 28	197	[156, 239]
Week 40	281	[240, 323]
Week 52	365	[324, 407]
Week 64	449	[408, 491]
Week 76	533	[492, 575]
Week 88	617	[576, 673]
Week 104	729	[674, 785 ^b]

Rx Day calculated relative to first dose date of risankizumab.

- a. Local tolerability not measured at Baseline and at Week 104. If time is collected in vital signs, restrict to records prior to the first dose of risankizumab.
- b. The minimum of upper bound and within 105 days of last dose of risankizumab.

Table 16. Visit Windows for Analysis of Safety Laboratory Tests and ECG in the ALL_RZB Population

Window Label	Target Day	Interval
Baseline	1	≤ 1
Week 4	29	[2, 71]
Week 16	113	[72, 155]
Week 28	197	[156, 239]
Week 40	281	[240, 323]
Week 52	365	[324, 407]
Week 64	449	[408, 491]
Week 76	533	[492, 575]
Week 88	617	[576, 673]
Week 104	729	[674, 785 ^a]

Rx Day calculated relative to first dose date of risankizumab.

a. The minimum of upper bound and within 105 days of last dose of risankizumab.

The time windows specified in [Table 17](#), [Table 18](#), [Table 19](#), [Table 20](#), [Table 21](#) and [Table 22](#) will be used for the summary of study drug injections of each period.

Table 17. Visit Windows for Summary of Study Drug Injections for Part A1

Window Label	Target Day	Interval

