For subjects who do not receive retreatment with risankizumab, TEAEs are defined as any event with an onset after the first dose of study drug in Part B and no more than 105 days after the last dose of study drug in Part B.

For subjects who receive retreatment with risankizumab, TEAEs are defined as any event with an onset after the first dose of study drug in Part B and before the first dose of retreatment with risankizumab.

TEAEs of Safety_B_PBO_RT and Safety_B_RZB_RT:

TEAEs are defined as any event with an onset that is after the first dose of retreatment and no more than 105 days after the last dose of study drug.

TEAE of ALL_RZB:

TEAEs are defined as any event with an onset after the first dose of risankizumab through 105 days after the last dose of risankizumab, except for AEs with an onset during protocol-designed treatment gaps (i.e., placebo period) that was more than 105 days from the last dose of the previous risankizumab treatment and before the first dose of retreatment.

Summary tables will be presented as follows:

1. Adverse Event Overview

The number and percentage of subjects experiencing treatment-emergent adverse events will be summarized for the following adverse event categories:

- Any AE
- Any AE that was assessed as related to study drug by the investigator
- Any severe AE
- Any serious AE (SAE)
- Any serious AE that was assessed as related to study drug by the investigator
- Any AE leading to discontinuation of study drug
- Any AE leading to death
- Any deaths
- Areas of Safety Interest

2. Adverse Events by System Organ Class and Preferred Term

TEAEs will be summarized and presented using primary Medical Dictionary for Regulatory Activities (MedDRA) system organ classes (SOCs) and preferred terms (PTs). The SOCs will be presented in alphabetical order, and the PTs will be presented in alphabetical order within each SOC.

Subjects reporting more than one adverse event for a given MedDRA preferred term will be counted only once for that term (most severe incident for the severity tables and most related incident for the relationship tables). Subjects reporting

more than one type of adverse event within a SOC will be counted only once for that SOC. Subjects reporting more than one type of adverse event will be counted only once in the overall total.

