11.3 Analysis of Laboratory Data

For the assessments of laboratory data, values observed more than 105 days after the last dose of study drug will be excluded.

Listing and descriptive statistics of laboratory values over time, changes from baseline, and extreme abnormal value on treatment will be provided. Extreme abnormal value is the value which is most significantly away from the reference range. Frequency of subjects with transitions relative to reference range and listing of subjects with significant abnormal laboratory values will be presented as well.

Analyses will be conducted in the Safety_A1 Population, the Safety_B_R Population, and the ALL_RZB Population.

For subjects who were re-randomized to placebo in Part B, laboratory values evaluated after 105 days from the last dose of risankizumab in Part A and before the first dose of retreatment will not be included in the summaries for the ALL_RZB Population.

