11.4 Analysis of Vital Signs and Weight

Analyses will be conducted in the Safety_A1 Population, the Safety_B_R Population, and the ALL_RZB Population.

For subjects who were re-randomized to placebo in Part B, vital sign values evaluated after 105 days from the last dose of risankizumab in Part A and before the first dose of retreatment will not be included in the summaries for the ALL_RZB Population.

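### In the pooled ALL_RZB safety population, ECG and local tolerability lack the placebo-gap exclusion that the SAP applies to adverse events, laboratory values and vital signs

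*SAP*

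**What the plan says.** SAP 5.1: ALL_RZB "is defined as all subjects who receive at least one dose of risankizumab in the study", and it is to receive complete safety tables. It therefore contains Arm 1 responders re-randomised to placebo at Week 28, whose last risankizumab dose before the gap is at Week 16. It also contains Arm 2 once those subjects cross over at Week 16.

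How the SAP treats the placebo gap in ALL_RZB, by type of data:

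| Data | Rule |
|---|---|
| Adverse events (11.2.1) | Removed: "except for AEs with an onset during protocol-designed treatment gaps (i.e., placebo period", where onset is more than 105 days after the preceding risankizumab dose and before retreatment |
| Laboratory (11.3) | Removed: "laboratory values evaluated after 105 days from the last dose of risankizumab in Part A and before the first dose of retreatment" |
| Vital signs (11.4) | Removed: "vital sign values evaluated after 105 days from the last dose of risankizumab in Part A and before the first dose of retreatment" |
| ECG (11.5) | No gap rule: "Analyses will be conducted in the Safety_A1 Population, the Safety_B_R Population, and the ALL_RZB Population" |
| Local tolerability (11.6) | No gap rule: "In addition, the overall rate (with at least one occurrence) during the study will also be presented in the ALL_RZB Population" |

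SAP 6.0 gives the ALL_RZB windows in Table 15 (vital signs and local tolerability) and Table 16 (laboratory tests and ECG). Both count days from the first risankizumab dose, and both carry the footnote "The minimum of upper bound and within 105 days of last dose of risankizumab". Protocol 5.3.5.1 places the local-tolerability assessment before dosing at dosing visits, so each assessment there reflects the previous injection.

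**The concern.** Three of five types of safety data have an explicit rule that keeps off-drug time out of the pooled risankizumab summary; two do not. A programmer who follows the text would leave off-drug ECGs and reactions to placebo injections in tables labelled risankizumab.

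The statistics involved make this more than a tidiness point. Section 11.5 reports each subject's maximum QTc and maximum change from baseline, and section 11.6 reports subjects with at least one occurrence. Extra off-drug observations can only raise figures of that kind. In the by-visit QTc means, off-drug values are simply averaged in with on-drug ones, and the distortion can go either way.

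**Working it through.** **1. The plan's own figure.** Protocol 7.7 and SAP 4.3 give 102:204 for 90% versus 75%, 1:2 allocation, two-sided 0.05 and 90% power. With pooled variance, k = 2 and mean rate (0.90 + 2 × 0.75)/3 = 0.80:

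n = [1.96 × √(1.5 × 0.80 × 0.20) + 1.2816 × √(0.90 × 0.10 + 0.75 × 0.25/2)]² / 0.15² = (0.960 + 0.549)² / 0.0225 ≈ 101.3, so 102 and 204.

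Then 306/0.8 = 382.5, rounded up to 383. The figure reproduces, so its inputs can be used for head counts.

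**2. Planned head counts.** Arm 1 is 400, with 80% responders at Week 28: 320 re-randomised. Two thirds go to placebo: 320 × 2/3 ≈ 213, or 43% of about 500 in ALL_RZB. Arm 2 adds 100 subjects with placebo injections at Weeks 0 and 4.

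**3. The gap in days.** The Week 16 dose is on Day 7 × 16 + 1 = 113. The 105-day limit then falls on Day 218, which is Week 31 (217/7 = 31.0). The Week 32 visit (Day 225) is 112 days after that dose.

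**4. What Tables 15 and 16 remove.**
- Arm 2's placebo period: days start at the first risankizumab dose, so Weeks 0 to 16 are baseline or earlier.
- Placebo-withdrawal subjects never retreated: their last risankizumab dose is Week 16, so data stop at Day 218.

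**5. What they leave in.** In a placebo-withdrawal subject who is retreated, the last risankizumab dose is a retreatment dose. The footnote limit moves behind the gap and the whole gap stays in. Days since the Week 16 dose are (relapse week − 16) × 7:

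| Relapse and retreatment at | Days since Week 16 dose | Days beyond 105 | Scheduled ECG windows in the gap before relapse |
|---|---|---|---|
| Week 32 | 112 | 7 | none |
| Week 40 | 168 | 63 | none |
| Week 52 | 252 | 147 | 40 |
| Week 70 | 378 | 273 | 40, 52, 64 |
| Week 82 | 462 | 357 | 40, 52, 64, 76 |

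The pre-dose ECG on the day of relapse adds one more. With retreatment at Week 64, the Week 40 and Week 52 ECGs lie (40 − 16) × 7 = 168 and (52 − 16) × 7 = 252 days after the dose.

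**6. How many subjects.** The documents give no retreatment share. The 25% in the sizing is loss of sPGA 0 or 1 by Week 52, which is not the same event as relapse (sPGA ≥ 3) by Week 88. Assumed shares of 10%, 25%, 50% and 100% of 213 give about 21, 53, 107 and 213 subjects, or 4%, 11%, 21% and 43% of ALL_RZB.

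**7. Effect on the local-tolerability rate.** The documents give no rate of reaction to placebo injections alone; I assume 2% to 10% of affected subjects.
- 53 affected: 53 × 0.02/500 to 53 × 0.10/500, or +0.2 to +1.1 percentage points.
- All 213 affected: +0.9 to +4.3 points.
- Literal study-wide reading, 213 + 100 = 313 affected: +1.3 to +6.3 points.

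**8. Would the 105-day rule suffice for local tolerability?** No. The Week 28 placebo injection (Day 197) comes 84 days after the Week 16 dose. A reaction to it recorded up to Day 218 is still within 105 days of risankizumab and would be counted.

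**The case against.** The strongest reply is that Table 15 is titled for local tolerability in ALL_RZB, and that the overall rate is the only ALL_RZB local-tolerability result that 11.6 specifies. On that reading the table must govern the rate, and the study-wide phrase is loose drafting. This is the more natural reading, and it stands as a limit on the size. It does not remove the problem, because the Table 15 footnote leaves the gap open in retreated subjects (step 5). The SAP's own structure points the same way. Laboratory data share Table 16 with ECG, and vital signs share Table 15 with local tolerability. If the footnotes were enough, the gap sentences in 11.3 and 11.4 would be unnecessary.

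A reader might go further and infer that placebo data from the whole study are certain to be reported as risankizumab. The supporting figures would be 63% of subjects (313/500), or a third of dosing visits: (100 × 2 + 213 × 6) = 1,478 placebo visits against 400 × 3 + 80 × 6 + 107 × 6 + 100 × 7 = 3,022 risankizumab visits, if nobody relapses. The documents do not support that as the expected case. Both figures need the study-wide phrase to override Table 15. The second assumes no relapse, which is exactly when the Table 15 footnote cuts every withdrawn subject at about Week 31. A share of dosing visits is also not the bias in a rate of subjects with at least one occurrence.

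Two mitigating points stand. Clinically relevant local findings are also reported as adverse events (Protocol 5.3.5.1), where the gap rule applies. Local reactions are expected to be uncommon (Protocol 2.3), so the shift in the rate is probably small.

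**Conclusion.** The omission is real for both ECG and local tolerability. Its firm core is the set of subjects re-randomised to placebo and later retreated: about 21 to 213 on planned numbers, depending wholly on an assumed retreatment share of 10% to 100%. For local tolerability the group grows to about 313 of 500 only if the study-wide wording is taken literally. That the text allows both readings is itself a reason to settle it.

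The consequence is confined to descriptive pooled safety summaries. The randomised comparisons in Safety_A1 and Safety_B_R are unaffected, as are all efficacy tests, alpha and sample size.

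Assumptions: planned head counts with no dropout; nominal visit days; and the Table 15 and 16 footnotes read as a limit on all the data, although the mark sits on the last window. The SAP does not say whether those tables also govern the maximum-QTc and overall-rate summaries, neither of which is a by-visit summary.

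**What to change.** - **SAP 11.5:** repeat for ECG the gap exclusion already in 11.3 and 11.4, and state that it also applies to the maximum QTc and maximum change summaries.
- **SAP 11.6:** for ALL_RZB, count an occurrence only when the most recent injection before the assessment was risankizumab. Replace the study-wide phrase with that rule. Copying the 105-day sentence is not enough, because it would still admit reactions to the Week 28 placebo injection recorded before about Week 31.
- **SAP 6.0:** say whether Tables 15 and 16 govern the overall and maximum summaries as well as the by-visit ones.

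Cost: two SAP sentences, one clarification, and a filter on the actual injection records. No new data are needed.

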12.0 Pharmacokinetic Analysis

Pharmacokinetic analysis is not covered in this SAP.

13.0 Biomarkers Analysis

Biomarker Analysis is not covered in this SAP.

14.0 Summary of Changes

14.1 Summary of Changes Between the Latest Version of Protocol and the Current SAP

- Defined analysis populations (including the Per-protocol population) in detail.
- Clarified independent null hypothesis test hierarchy in the ITT Population in Part B consisting re-randomized subjects.
- Added additional ranked secondary endpoint to the ITT Population in Part B consisting re-randomized subjects: achievement of sPGA of clear or almost clear (0 or 1) at Week 104.
- Pre-specified Areas of Safety Interest.

14.2 Summary of Changes Between the Previous Version and the Current Version of the SAP

Updated Table 25, Table 27, and Table 28 based on Integrated Summary of Safety SAP.

Updated the end day for inclusion concomitant medications, based on Integrated Summary of Safety SAP.

15.0 Appendix

None.

17.0 List of Tables, Figures and Data Listings That are to Be Programmed

To be provided in a separate document.
